7.6. Treatment Compliance

Patient compliance with study drug will be assessed at each visit. LY3405105 compliance will be assessed by direct questioning, counting returned capsules/tablets/packages, and reviewing patient diaries. Deviations from the prescribed dosage regimen should be recorded on the CRF.

A patient will be considered significantly noncompliant if he/she misses more than 20% cumulative days of study medication (full doses) during each cycle. A patient may be considered significantly noncompliant if he or she is judged by the investigator to have intentionally or repeatedly taken more than the prescribed amount of medication.

7.6.1. **Evaluable Patients**

Patients who withdraw from the study before receiving study drug(s) will be replaced and will not be included in the safety or efficacy assessments. Safety analyses will be conducted on all patients who have received at least 1 dose of study drug, regardless of whether they are deemed evaluable for the assessment of a dose level.

Any patient who is discontinued from the study before receiving at least 80% of LY3405105 planned doses in Cycle 1 will be deemed non-evaluable for assessment of safety at that dose level and may be replaced unless they experience a DLT or dose omission/reduction due to toxicity prior to withdrawal. A patient may be deemed non-evaluable for assessment of a dose level in the event the patient experiences an AE which would meet DLT criteria, and furthermore has been determined through discussion between investigator and Lilly CRP/CRS to most likely be related to a concomitant medication or a prior line of immune therapy (in the case of immune-related AEs) due to previously established linkage.

If the patient is noncompliant during Cycle 1 due to reasons other than drug-related toxicity, he or she will be considered non-evaluable and may be replaced.

Non-evaluable patients may be replaced to ensure that at least 3 patients complete 1 cycle of therapy at each dose level, unless accrual to that dose level has stopped due to a DLT.

Patients who are not evaluable for PK, but who complete 1 cycle of therapy, may be replaced upon consultation with the investigator(s) and the Lilly CRP/CRS to ensure adequate PK data, unless accrual to that dose level has stopped due to a DLT.

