8.1. Discontinuation from Study Treatment

Patients will be discontinued from study treatment in the following circumstances:

- the patient is enrolled in any other clinical study involving an investigational product or any other type of medical research judged not to be scientifically or medically compatible with this study
- the patient becomes pregnant during the study
- the patient is significantly noncompliant with study procedures and/or treatment as described in Section 7.6
- the patient has confirmed progressive disease

Exception: Patients with documented progressive disease may be allowed to continue LY3405105 if the patient is tolerating treatment and, in the opinion of the investigator, is deriving clinical benefit from continuing study treatment and continuation of treatment is approved by the Sponsor.

- the patient experiences unacceptable toxicity
- the patient has had 2 dose reductions and experiences an AE that would cause a third dose reduction
- the investigator decides that the patient should be discontinued from study treatment
- the patient requests to be discontinued from study treatment
- the patient's legal representative requests that the patient be discontinued from study treatment.

Patients who are discontinued from study treatment will have follow-up procedures performed as shown in the Schedule of Activities (Section 2).

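### Protocol 7.6.1 keeps a DLT in a patient who leaves the study early but not in one who is noncompliant in Cycle 1, and no defined analysis set settles which rule governs

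*Protocol*

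**What the plan says.** Protocol 7.6.1 has two adjacent rules on who counts in the assessment of a dose level.

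- **Early discontinuation.** A patient discontinued from the study before receiving 80% of the planned Cycle 1 doses is non-evaluable and "may be replaced unless they experience a DLT or dose omission/reduction due to toxicity prior to withdrawal".
- **Noncompliance.** If a patient is "noncompliant during Cycle 1 due to reasons other than drug-related toxicity, he or she will be considered non-evaluable", and replacement is permitted. Nothing is said about a DLT.

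Protocol 7.6 defines significant noncompliance in two ways: a patient who "misses more than 20% cumulative days of study medication (full doses) during each cycle", and, at the investigator's judgement, one who has "intentionally or repeatedly taken more than the prescribed amount of medication".

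Three other provisions bear on the point. Replacement of non-evaluable patients, to reach three who complete a cycle, is allowed "unless accrual to that dose level has stopped due to a DLT". Safety analyses take in every treated patient, "regardless of whether they are deemed evaluable for the assessment of a dose level". Protocol 8.1 stops study treatment when "the patient is significantly noncompliant with study procedures and/or treatment as described in Section 7.6"; leaving the study is a separate matter under 8.2.

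Protocol 10.2 defines safety, PK and biomarker populations only. SAP 6.3 refers to patients evaluable for DLT but does not define them.

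**The concern.** The qualifier in the noncompliance rule describes why doses were missed, not what happened to the patient. Someone who misses a week of treatment for an unrelated reason and also has a DLT in Cycle 1 falls squarely under it. The wording makes non-evaluability mandatory; only replacement is discretionary.

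For a missed-dose patient this runs in the unsafe direction. A DLT at less than the planned exposure is evidence that the full dose is at least as toxic. Leaving it out lowers the observed DLT rate. If it is also left out of the N-CRM, it raises the highest dose the model will recommend, which Protocol 7.1.1.2 treats as a ceiling.

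**Working it through.** The plan states no figure that depends on this rule, so there is nothing of its own to reproduce. The check has two parts.

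**1. Reading the rules together**

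- The missed-dose threshold is 0.20 × 28 = 5.6, so 6 or more missed days. A patient who misses exactly 6 has taken 22/28 = 78.6%, which is also under 80%. The two rules therefore cover the same range of exposure.
- A noncompliant patient who stays on study, or who stops treatment under 8.1 without leaving the study, meets only the noncompliance rule. A DLT does not keep that patient evaluable.
- A noncompliant patient who also leaves the study before 80% of doses and had a DLT meets both rules, and they give opposite answers.
- Protocol 7.1.1.1 speaks of confounded cases as not evaluable for dose selection, and 10.3.4 times the Phase 1a interim analysis by patients evaluable for dose-level assessment. Both imply that non-evaluable patients do not inform dose selection. Protocol 7.1.1.2 says only that the model is fitted to the data at the end of each dose level.

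**2. Can one omitted DLT matter?**

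Inputs from Appendix 7: the two-parameter logistic model, logit p(d) = log α + β·log(d / 1 mg), with (log α, log β) bivariate normal, means −3.88 and −0.11, standard deviations 2.85 and 0.17, correlation −0.88; and the limits P(p > 0.33) < 0.25 and P(p > 0.60) < 0.05. Dose levels are the examples in Table JZFA.7.1. Assumption: 0/3 DLTs at each lower level. The posterior is the prior times the binomial likelihoods, evaluated on an 801 × 801 grid.

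The comparison must hold the number of treated patients fixed. If one DLT patient is dropped and replaced, the data with that patient counted have one more DLT and one more patient.

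| Current → next dose | DLT counted | P(p > 0.33) at next dose | DLT dropped and replaced | P(p > 0.33) at next dose |
|---|---|---|---|---|
| 8 → 15 mg | 2/7 | 0.307 (barred) | 1/6 | 0.116 (allowed) |
| 4 → 8 mg | 2/7 | 0.334 (barred) | 1/6 | 0.125 (allowed) |
| 15 → 30 mg | 1/4 | 0.213 (allowed) | 0/3 | 0.041 (allowed) |

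P(p > 0.60) at the next dose is below 0.02 in all six cells, so the 25% limit decides each one.

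**Sensitivity to the prior.** The printed parameters give median DLT probabilities of 0.020 at 1 mg and 0.306 at 30 mg, against the stated 0.01 and 0.28. I shifted the means to match either or both stated medians. The 8 → 15 mg pair then ranges over 0.262 to 0.363 counted and 0.090 to 0.144 dropped. The 4 → 8 mg pair ranges over 0.291 to 0.378 and 0.099 to 0.144. Both pairs still cross 0.25. The single-DLT case (1/4 at 15 mg) ranges over 0.169 to 0.271, on both sides of the limit, so it is not a stable example either way.

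**How often.** The documents give no noncompliance rate. Assume unrelated noncompliance in a fraction q of patients, independent of DLT. The chance that at least one DLT among 6 patients falls under the rule is 1 − (1 − pq)⁶:

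- p = 0.20: 0.059 at q = 0.05 and 0.217 at q = 0.20.
- p = 0.33: 0.095 at q = 0.05 and 0.336 at q = 0.20.

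This is the chance of omitting a DLT, not of changing a decision.

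**The case against.** The strongest reply is that the gap is narrow and the DLT stays in view. Noncompliance caused by drug toxicity is already exempt, and Table JZFA.7.2 requires suspension for many severe toxicities, so most days missed after a DLT fall outside the rule. All treated patients remain in the safety analyses, escalation needs agreement between sponsor and investigators, and Protocol 10.3.2 rests the final RP2D on review of all DLTs. All of this stands, and it limits the consequence. None of it makes the patient evaluable again when the dose-level decision is taken.

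Two stronger readings are tempting and are not supported.

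- A reader might infer that the plan states that such a DLT is removed from the N-CRM. It does not; this is inferred from 7.1.1.1 and 10.3.4.
- A reader might infer that a single dropped DLT flips the decision, by setting 1/3 at 15 mg (0.260, barred) against 0/3 (0.041, allowed). That compares three treated patients with four. Like for like it is 1/4 against 0/3, and under the printed prior both allow 30 mg.

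A blanket DLT exception would also be wrong. The same sentence reaches patients who took more than prescribed, and their DLT would then be charged to a dose they exceeded.

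**Conclusion.** The inconsistency in 7.6.1 is real and should be corrected. For missed doses unrelated to toxicity, the text makes a patient with a DLT non-evaluable, while the neighbouring rule keeps a comparably under-dosed patient who left the study. No analysis set resolves the difference.

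The effect is a downward bias in the DLT rate used at the dose-level decision. In the 8 mg example the observed rate falls from 2/7 (29%) to 1/6 (17%), and a barred escalation becomes allowed. This rests on an example prior, on 0/3 at lower levels, on non-evaluable patients being left out of the model, and on the 25% limit. Under the 40% limit that Appendix 7 applies after Cohort 8, neither 2/7 case would be barred. The situation should be uncommon, but its frequency cannot be derived from the documents.

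**What to change.** In the noncompliance sentence of 7.6.1, add for missed-dose noncompliance only that the patient remains evaluable if a DLT occurs, as the early-discontinuation rule already provides. State separately that DLTs in patients who took more than prescribed are reviewed individually, with the decision documented.

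Define one DLT-evaluable set in Protocol 10.2 and in the SAP, use it wherever evaluability for DLT or dose level is mentioned, and name it as the input to the N-CRM.

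The cost is small: one clause, one sentence and one definition. A DLT with incomplete dosing would count at the assigned dose, which is slightly conservative. No dose, schedule or treatment rule changes.

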7.7. Concomitant Therapy

The list of excluded medications and procedures is provided in [Appendix 4](#).

No other chemotherapy, radiotherapy, immunotherapy, cancer-related hormone therapy, experimental drugs, or herbal supplements will be permitted while the patients are on this study.

The need for any form of radiotherapy (including palliative) will be cause for early discontinuation from the study.

Patients should refrain from consuming grapefruit, grapefruit juice, and grapefruit-containing products while on study.

In addition, any disease progression requiring other forms of specific anti-tumor therapy will also necessitate early discontinuation from the study. Appropriate documentation for all forms of premedication, supportive care, and concomitant medications must be captured on the case report form. Replacement hormonal therapy initiated before study entry will be allowed.

If clinically indicated at any time during the study, erythropoietin and packed red blood cell transfusions may be used according to American Society of Clinical Oncology (ASCO) guidelines (Rizzo et al. 2008). Prophylactic antibiotic treatment should be consistent with ASCO guidelines (Flowers et al. 2013).

Patients on stable doses of bisphosphonates or denosumab are allowed to continue. These agents should not be initiated within the 2 weeks prior to study enrollment or at any point while on the study.

All concomitant medications should be recorded throughout the patient's participation in the study.

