7.8. Treatment After the End of Study

The end of study definition is defined in Section 5.3. Investigators will continue to follow the schedule of activities provided in Section 2 until notified by Lilly that end of study has occurred.

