7.8.1. Treatment After Study Completion

Study completion will occur following the final analysis of primary and secondary objectives, as determined by Lilly. Investigators will continue to follow Schedule of Activities (Section 2) for all patients until notified by Lilly that study completion has occurred.

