8.2. Discontinuation from the Study

Patients will be discontinued from the study (including follow-up procedures) in the following circumstances:

- participation in the study needs to be stopped for medical, safety, regulatory, or other reasons consistent with applicable laws, regulations, and good clinical practice (GCP)
- the patient becomes pregnant during the study. See Section 9.2 regarding regulatory reporting requirements on fetal outcome and breastfeeding
- the investigator decides that the patient should be discontinued from the study
- the patient requests to be discontinued from the study
- the patient's legal representative requests that the patient be discontinued from the study.

Patients who discontinue from the study early will have end-of-study procedures performed as shown in the Schedule of Activities (Section 2).

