Appendix 4. Restricted and Prohibited Concomitant Medications

The table below describes the drug class and associated medications that will be restricted during the study treatment period. Patients who, in the assessment by the investigator, require the use of any of the prohibited treatments for clinical management should be removed from the study.

This is not an all-inclusive list. In general, strong CYP3A4 inhibitors, strong inducers of CYP3A4, or P-gp, are restricted during the study treatment period.

Strong Inhibitors of CYP3A4

All HIV protease inhibitors
Boceprevir
Clarithromycin
Conivaptan
Danoprevir and ritonavir
Diltiazem
Elvitegravir and ritonavir
Idelalisib
Itraconazole
Ketoconazole
Nefazodone
Paritaprevir and ritonavir and (ombitasvir and/or dasabuvir)
Posaconazole
Telaprevir
Troleandomycin
Voriconazole

Strong Inducers of CYP3A4

Aminoglutethimide
Apalutamide
Avasimibe
Carbamazepine
Enzalutamide
Fosphenytoin
Lumacaftor
Mitotane
Phenobarbital
Phenytoin
Rifabutin
Rifampicin (rifampin)
Rifapentine
St. John's wort

Abbreviation: HIV = human immunodeficiency virus.

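### Protocol 7.7 and Appendix 4 take patients off the study, which under 8.2 ends follow-up, while 5.1.3, 7.8.1, 8.1 and the Schedules continue it (minor)

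*Protocol*

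**What the plan says.** The protocol has two kinds of exit.

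- **Study treatment (8.1).** Confirmed progression is on this list. Patients who stop treatment go on to the follow-up in the Schedule of Activities.
- **The study (8.2).** "Patients will be discontinued from the study (including follow-up procedures) in the following circumstances". The list includes the patient's request, the investigator's decision, and a general item: "participation in the study needs to be stopped for medical, safety, regulatory, or other reasons".

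Three conditions elsewhere use the language of the second exit:

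- Protocol 7.7, radiotherapy: "The need for any form of radiotherapy (including palliative) will be cause for early discontinuation from the study".
- Protocol 7.7, progression: "any disease progression requiring other forms of specific anti-tumor therapy will also necessitate early discontinuation from the study".
- Appendix 4: patients who need any of the "prohibited treatments for clinical management should be removed from the study".

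Other passages keep follow-up going. Section 5.1.3 ends the post-treatment period only at death, loss to follow-up or overall study completion. Section 7.8.1 says: "Investigators will continue to follow Schedule of Activities (Section 2) for all patients until notified by Lilly that study completion has occurred". Tables JZFA.2.1 and JZFA.2.2 schedule survival checks every 3 months after treatment, by telephone if needed, and imaging until radiographic progression, death or study completion.

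On the analysis side, Protocol 10.3.1 and SAP 6.7.1 censor OS at the last date known alive, expressly including patients withdrawn from the study. SAP 6.7.2 summarises OS, PFS, DoR and TTR descriptively by Kaplan-Meier, in Phase 1b only.

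**The concern.** A site cannot apply 7.7 or Appendix 4 as worded, give the exit its 8.2 meaning, and also carry out the follow-up in 5.1.3 and the Schedules.

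If a site follows 7.7 literally, survival contacts stop when a progressing patient needs further therapy. OS is then censored close to progression, in patients whose hazard of death differs from that of patients still at risk. Kaplan-Meier assumes that this does not happen. For radiotherapy or a prohibited drug before progression, scans stop as well, so PFS and DoR are censored early. Under the plan's own censoring rules only subsequent *systemic* anticancer therapy ends the usable assessments, so scans after radiotherapy alone would otherwise have counted.

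Sites that read the passage differently would also code the same event differently. SAP 6.3 reports reasons for leaving treatment and for leaving the study separately, and the SAP 6.14 participant flow rests on study discontinuation.

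**Working it through.** The point is textual, and the plan states no figure to reproduce. The passages compare as follows for each trigger.

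| Trigger | 7.7 / Appendix 4 | 8.1 | 8.2 | 5.1.3, 7.8.1, Schedules |
|---|---|---|---|---|
| Progression needing other anti-tumor therapy | leaves the study | confirmed progression ends treatment; follow-up continues | not named | survival checks continue; scans end at radiographic progression |
| Any radiotherapy | leaves the study | not named | not named | survival checks continue; scans continue until radiographic progression |
| Prohibited drug | removed from the study | not named | not named | same as radiotherapy |

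Three things follow.

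1. *Progression.* This is a contradiction between passages and not a missing rule. Sections 8.1 and 5.1.3 and the Schedules answer the question one way, and 7.7 answers it the other way. Few scans are at stake, because they stop at radiographic progression anyway; survival contacts are what could be lost.
2. *Radiotherapy or a prohibited drug before progression.* Section 8.1 names neither, so only the general follow-up passages stand against 7.7 and Appendix 4. Both scans and survival contacts could be lost.
3. *Registry flow.* SAP 6.14 counts a patient observed until progression or death as completing, so only patients removed before progression could lose that status.

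**Purely hypothetical size.** The documents give no removal share and no survival times, so every input here is assumed. First events are exponential with median m1 (rate h1 = ln2/m1). A share p of them are deaths and the rest are progressions. Death after progression is exponential with median m2 (h2 = ln2/m2). A share f of progressing patients is censored at progression.

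- Event-free: S1 = exp(−h1·t)
- Alive after progression: Prog = (1−p)·h1·[exp(−h2·t) − exp(−h1·t)]/(h1−h2), taking the limit when h1 = h2
- True OS: S1 + Prog
- Kaplan-Meier limit: exp(−∫ [p·h1·S1 + (1−f)·h2·Prog] / [S1 + (1−f)·Prog] dt)

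Example: m1 = 2.5 (h1 = 0.277), m2 = 6 (h2 = 0.116), p = 0.15 and f = 0.5. True median OS is 8.55 months and the Kaplan-Meier limit is 9.49, a shift of +0.94.

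Grid of 75 cells: m1 in {2, 2.5, 3, 3.5, 4}, m2 in {4, 5, 6, 7, 8}, p in {0, 0.15, 0.30}.

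| Share removed f | Shift in median OS, months (min / middle / max) | Shift in 12-month OS, points (middle cell) |
|---|---|---|
| 0% | 0 / 0 / 0 | 0 |
| 5% | −0.01 / +0.08 / +0.17 | +0.37 |
| 10% | −0.03 / +0.17 / +0.36 | +0.78 |
| 25% | −0.08 / +0.48 / +1.03 | +2.22 |
| 50% | −0.19 / +1.22 / +2.76 | +5.55 |

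The shift is downward in 2 of 75 cells at each non-zero share. For scale, the simulated standard deviation of a fully followed 20-patient Kaplan-Meier median is 2.0 to 2.5 months. The table shows only that the result depends on f, which the documents do not give.

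**The case against.** The strongest reply is that the plan as a whole plainly intends follow-up to continue, and that 7.7 is loose drafting in a concomitant-therapy section. Much supports this:

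- Section 8.1 puts confirmed progression under treatment discontinuation, with follow-up.
- Section 7.8 says: "Investigators will continue to follow the schedule of activities provided in Section 2 until notified by Lilly that end of study has occurred". Section 7.8.1 extends this to all patients.
- Appendix 4 sets its own scope: "The table below describes the drug class and associated medications that will be restricted during the study treatment period".
- Section 7.6.1 already speaks of discontinuing from the study when it means not completing Cycle 1 dosing.
- The PFS, DoR and TTR rules expect later systemic therapy, and SAP 6.14 expects patients to be in follow-up after treatment.
- Section 8.2 names none of the three triggers. Its investigator-decision and other-reasons items are discretionary and exist whatever 7.7 says; 8.1 has a parallel investigator-decision item.

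Most of this stands. A reader might infer from 7.7 that the protocol stops survival follow-up at progression, or that nothing in it governs follow-up after progression. The documents support neither inference, because 8.1, 5.1.3 and the Schedules provide for that follow-up.

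What remains is that no passage says 7.7 or Appendix 4 means treatment only, or that 8.1 prevails over 7.7, which is the more specific rule for progression needing other therapy. The 8.2 general items leave room for a literal reading. The closing line of 8.2, on end-of-study procedures, does not settle the matter, since neither Schedule has a column of that name. For radiotherapy and prohibited drugs, 8.1 gives no direct answer.

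**Conclusion.** The contradiction is real and its impact is minor. Context favours reading 7.7 and Appendix 4 as ending treatment only, most clearly for progression and least clearly for radiotherapy or a prohibited drug before progression.

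Harm arises only if sites apply the wording literally. In that case OS, and to a lesser extent PFS and DoR, would be informatively censored, and study-discontinuation counts would be inconsistent. These endpoints are secondary and descriptive, with no decision rule attached. The primary endpoints (safety and DLTs in Phase 1a, ORR in Phase 1b) are essentially unaffected.

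A reader might also take the hypothetical grid as evidence of an inflated OS. It is not: the removal share and survival times are assumed, and at small shares the shift is negligible. The documents do not allow the bias to be sized. The case for correcting the text is that deaths not collected may not be recoverable later and that the correction costs almost nothing.

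**What to change.** Reconcile both sentences of Protocol 7.7, and Appendix 4, with 5.1.3, 7.8.1, 8.1, 8.2 and Section 2. One sentence would do, for example: *Meeting a condition in Section 7.7 or Appendix 4 does not by itself end scheduled survival follow-up, or scheduled imaging until radiographic progression; these end early only for a separate Section 8.2 reason, such as the patient's own request.*

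This concerns follow-up only and alters no clinical trigger for stopping treatment. The cost is one sentence in an amendment or a site memo. No procedure is added, since the survival contacts and scans are already in the Schedules of Activities.
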